The current standard of care for the treatment of chronic pain in people with sickle cell disease is the use of both long and short acting opiates. Full agonists are opioid drugs that bind completely to mu opioid receptors in the brain, and cause them to produce endorphins which relieve pain [12]. The best approach to the treatment of chronic pain in people with sickle cell disease is unclear and there is little literature on the effectiveness of chronic opioid therapy in this patient population. In a recently published paper we compared pain symptoms in 83 adults who were either on chronic opioid therapy or not. We found that those on chronic opioid therapy exhibited greater levels of clinical pain, central sensitization as well as higher levels of healthcare utilization. This suggested that despite the use of opioid therapy, patients continued to have a very high symptom burden.

As with any persistent use of opiates for other chronic pain conditions, there is an increase probability of opioid dependency and in rare cases, an increased probability of aberrant opioid use. Opioid induced hyperalgesia, central sensitization and refractory pain are potential long-term outcomes for many SCD patients on long term opioids, potentially leading to higher doses of opioids over time [11]. Therefore, there may be great value in reducing the use of full agonist opioids for patients with sickle cell disease.

There are only three therapies available to decrease vaso-occlusive crisis (VOC); stem cell transplant, chronic transfusion therapy and hydroxyurea. Transplant is the only known cure for this disease; its safety and efficacy, especially in adults, remains a concern and is only available to adults as a research protocol. Chronic transfusion therapy is an effective way of decreasing the risk of several complications of SCD including stroke and VOC events [13]. Hydroxyurea is an effective disease-modifying therapy that decreases the risk of VOC by 50%. However, neither chronic transfusions nor hydroxyurea have been shown to decrease the prevalence of chronic pain. There is a subset of patients who are on effective disease modifying therapy, yet continue to have frequent acute visits for parenteral opioids and are maintained on high dose oral opioids as outpatients.

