Prior to enrolling on this trial participants will have already made a decision to convert to buprenorphine therapy after lengthy discussions with the clinical care team. That discussion includes risks and benefits of buprenorphine and the need to be in mild- moderate withdrawal prior to initiating buprenorphine. In addition, most patients will be weaned down as much as possible from their current opioid dose prior to initiating the protocol below.

- a. Study design, including the sequence and timing of study procedures.
 1. **Within 90 days prior to day 0** subject will sign Informed Consent Form (ICF) (R) , have urine toxicology testing, and complete HRQoL tool (ASCQ-Me) (R),brief pain inventory (BPI) (R), the PROMIS Pain Interference – Short Form instrument (R), and the PROMIS Physical Function – Short Form instrument (R). The ASCQ-Me tool is a validated health related quality tool for use specifically in SCD. The PROMIS Pain Interference instrument measures the degree to which pain hinders social engagement and life enjoyment. The PROMIS Physical Function instrument measures the degree to which pain affects everyday physical activities.
 2. Data will be collected on acute care utilization, sickle cell disease co-morbidities from chart abstraction and recorded in case report forms.
 3. **Day 0:**
 - a. Subject will complete ASCQ-Me, PROMIS Pain Interference, PROMIS Physical Function, and BPI with 7 day anchor (R).
 - b. Prior to discharge from SCIC subject will have COWS assessment, pain rating collected.
 4. **Day 1:** Subject will return to repeat COWS.
 5. Subject will return **day 14, day 30, day 90, and day 180** to repeat ASCQ-Me, PROMIS Pain Interference, PROMIS Physical Function, and BPI (R), or subject will complete these surveys over the phone or online on those days in lieu of coming for a study visit. Acute care utilization will be collected from subject, medical record and Crisp.

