- a. The only change in the ICF version approved by IRB on November 6 2019 was the option of completing the study surveys remotely (over the phone or online) for participants. Patients that were consented using a previous version of the ICF and are enrolled to the study before the November version, have agreed to all study procedures, but have not agreed to having the option to complete the study surveys online or over the phone. The study team will reach out to these **currently enrolled patients** during in-person clinical visits, via telemedicine appointments or over the phone to re-consent them to the study in-person or remotely using the ICF version approved on November 6 2019. On the instances when the re-consent process is done remotely, the person obtaining the re-consent will:
 - i. Sign, print their name, and add date and time of the re-consent, under the consent line.
 - ii. Add on the line of the patient signature: *[First and Last name of patient]* provided verbal affirmation of this newer version of their previously signed consent (the only change from previous signed version by patient is that the surveys can be completed remotely).
- 6. Data will be extracted from EPIC and CRISP on health care utilization for the 6 months prior to enrollment and 3 years post conversion.
- 7. We will also collect data on the 15-20 patients that we have now converted to buprenorphine. We will retrospectively review charts to collect genotype data, acute care utilization (ED, sickle infusion clinic and hospitalizations), COWS scores, sex, age and any complications that occurred with conversion. These subjects will be asked to complete ASCQ-Me and Promis tools.
- b. (distinguish research procedures from those that are part of routine care).
All research activities are noted with (R) above.
- c. Study duration and number of study visits required of research participants.
Each participant will be enrolled for 3 years and will have up to 6 study visits with the possibility of completing the ASCQ-Me, BPI and Promis tools over the phone or online instead of coming in for a study visit. The initial visit is part of routine care that we provide for conversion from opioids to buprenorphine.
- d. Blinding, including justification for blinding or not blinding the trial, if applicable. NA
- e. Justification of why participants will not receive routine care or will have current therapy stopped.
NA
- f. Justification for inclusion of a placebo or non-treatment group. NA

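### The only stated pre-conversion utilization window, the 6 months before enrollment, may coincide with the spell that prompted conversion, so regression to the mean could mimic a fall in acute care

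*Combined protocol and SAP*

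**What the plan says.** Item 6 of the study design list provides for an EPIC and CRISP extraction covering "health care utilization for the 6 months prior to enrollment and 3 years post conversion". No other pre-conversion period for utilization is stated in the text available for review; a portion just before the study design list was not available.

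The paragraph introducing the study design says that "participants will have already made a decision to convert to buprenorphine therapy after lengthy discussions with the clinical care team", and that "most patients will be weaned down as much as possible from their current opioid dose prior to initiating the protocol". Consent and baseline surveys are placed "Within 90 days prior to day 0". The Abstract and Background describe a subset of patients on effective disease-modifying therapy who "continue to have frequent acute visits for parenteral opioids" and remain on high-dose oral opioids.

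Section 5 sets no utilization threshold; entry depends on being converted. The item on a placebo or non-treatment group is answered NA. Section 7 lists decreased acute care utilization among the secondary outcomes and plans a paired t-test, pre against post, with no covariate, trend or control series. For the 15-20 patients already converted, Section 2 plans a pre/post utilization comparison, but item 7 of the study design list gives no window for it.

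**The concern.** A count taken over one short period is part usual rate and part chance or passing flare. If patients are more likely to choose conversion after an unusually heavy spell, and the baseline is that same spell, their later counts will tend to drift back towards their usual rate whatever the treatment does. A paired test cannot tell this drift from a drug effect, and there is no comparator to reveal it.

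The plan has the features that allow this: a single 6-month window just before entry, entry through a prior treatment decision, a target group described by frequent acute visits, and an unadjusted test of an endpoint worded as a decrease. At stake is whether a reported fall in acute care can be read as a benefit of conversion.

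The wean raises a different problem. If it falls in the window, the baseline does not represent stable full-agonist use, and utilization could be pushed either up or down.

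**Working it through.** **Inputs from the protocol.** Pre window 6 months, ending at enrollment; post window 3 years from conversion; no comparator; paired t-test; 15-20 patients already converted. The protocol states no visit rate, variance, alpha, power or prospective sample size, so there is no planned figure to reproduce. Everything below is illustrative, with zero treatment effect throughout.

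**1. By hand.** Let each patient's rate per 6 months be gamma distributed with mean m and shape k, with Poisson counts. The correlation between two 6-month windows is r = m/(m + k). If the patients who convert have mean pre count p, and selection acts only through that count:

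- expected post count = m + r(p - m)
- apparent fall = 1 - post/p = (1 - r)(1 - m/p)

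Taking p from simulated selection rules:

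- No selection: p = m, so the fall is 0%.
- m = 6, k = 1, probability of converting rises mildly with the count: r = 6/7 = 0.857, p = 9.43, post = 6 + 0.857 × 3.43 = 8.94, fall = 5.2% (simulated 5.3%).
- m = 3, k = 1, top quarter converts: r = 3/4 = 0.75, p = 6.98, post = 3 + 0.75 × 3.98 = 5.985, fall = 14.3% (simulated 14.3%).
- m = 3, k = 2, top quarter: r = 3/5 = 0.60, p = 6.08, post = 3 + 0.60 × 3.08 = 4.848, fall = 20.3% (simulated 20.1%).

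**2. Adding passing flares.** An independent gamma factor (shape 2) for each 6-month window lowers the between-window correlation to 0.31-0.46 and enlarges the fall, up to 38%. Over all settings (m = 3 or 6; k = 1 or 2; with or without flares), the fall was about 0% with no selection and 5% to 38% under mild to top-quarter selection. A second set of inputs (mean 3-12 visits per 6 months, between-patient CV 0.7, within-patient CV 0.3-0.7, selection of the top half or top quarter on the last 6 months) gave roughly 8% to 40%. Selection on each patient's long-run rate gave about 0%.

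**3. Effect on the test.** Paired t-test of the 6-month pre count against the mean 6-month count over 3 years post, two-sided 5% (assumed), so 0.025 is nominal for a fall. Probability of a significant fall, using the settings in steps 1 and 2 with m = 3 or 6:

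| Selection on last 6 months | n = 15 | n = 20 | n = 40 (assumed) |
|---|---|---|---|
| None | 0.01-0.02 | 0.01-0.02 | 0.01-0.02 |
| Mild to top quarter | 0.05-0.75 | 0.06-0.86 | 0.11-0.99 |

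The long follow-up does not help: falls measured at 6 months and over 36 months agreed within 0.3 points, because the bias sits in the baseline.

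**4. Does an earlier baseline help?** Apparent fall against months -24 to -7:

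- Selection on the last 6 months, flares independent between windows: about 0%.
- The same, but flares persist from one window to the next: up to about 6%.
- Selection on use over the whole prior 24 months: the fall of roughly 5% to 21% was not reduced at all.

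**5. Windows.** The post window is 36/6 = 6 times the pre window. An unchanged rate of 3 visits per 6 months gives totals of 3 and 18, so a common rate scale is needed before any paired test. If enrollment is dated at consent, up to 90 days before day 0 fall in neither window.

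**The case against.** The strongest reply is that the selection is assumed. The protocol does not date the decision to convert, and it sets no utilization threshold. Its description of the target group reads at least as much like persistent high use as like a recent spike: frequent visits continue despite effective disease-modifying therapy. It also gives inability to wean and evidence of opioid use disorder as reasons for conversion. If patients converted because of their long-run rate, or for reasons unrelated to recent visits, there is no regression effect to find. The study is also labelled descriptive and observational, and its primary endpoint is safety.

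Much of this stands. A reader might infer that the 6-month window is the period in which patients decided, or that an inert treatment would necessarily show a fall. The documents support only that it may be that period and that a fall could appear. A reader might also take utilization to be the main measure of benefit; it is one of several secondary measures, alongside BPI, ASCQ-Me and PROMIS. Nor can the same flaw be asserted for the 15-20 patients already converted, because no window is stated for them.

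What does not stand is the descriptive label as a full answer. Section 7 specifies a significance test on an endpoint worded as a decrease, and Section 2 names benefit as part of the purpose. The plan as written offers no means of telling whether selection on recent use occurred.

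**Conclusion.** The point holds as a possibility that the design leaves open. With one short baseline just before entry, no comparator and an unadjusted paired test, regression to the mean could produce an apparent fall in acute care without any effect of conversion.

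Its size cannot be computed from the documents. Under assumed visit rates it is about 0% if conversion did not depend on recent use, and roughly 8% to 40% if it depended strongly on the last 6 months; milder dependence gave as little as 5%. These figures rest on assumed rates, variation between and within patients, and selection rules. The wean adds a separate distortion whose direction and timing are not known.

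A reader might infer that moving the baseline back cures the problem. It does so only if heavy spells are short and selection was on the last 6 months.

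**What to change.** - Extend the EPIC/CRISP extraction to 24 months before conversion, after confirming that consent or IRB approval covers the earlier records.
- Anchor all windows at day 0, and apply the same windows to the 15-20 patients already converted.
- Express utilization as visits per month in every window.
- Report the post-conversion rate against months -24 to -7 beside the planned 6-month contrast.
- Show months -6 to 0 separately in a month-by-month plot. This period includes the gap of up to 90 days between enrollment and day 0.
- State in Section 7 that benefit will not be claimed from the 6-month contrast alone. State also that the earlier baseline reduces regression to the mean but may not remove it if high use persisted or selection was on longer-term use.

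The cost is a longer date range in an extraction already planned, some protocol wording, and the consent or IRB check. It adds no visits. The downsides are less complete older records, more exposure to time trends in disease or practice, and probably a smaller reported fall.

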Most relevant to SCD patients on high doses of opioids, there has been recent data on successful conversion for patients with chronic pain who are on high-dose opioids, from 100mg to 400mg morphine equivalents, to SL buprenorphine. This study reported a decrease in pain scores after the initiation of SL buprenorphine therapy for more than two months. Our goals of this study is to assess patient important outcomes post conversion to buprenorphine.

2. Objectives

The purpose of this study is to assess the safety and benefit of converting adults with sickle cell disease on high dose opioid therapy with evidence of opioid use disorder to buprenorphine. The primary outcome will be to assess the safety of the protocol. Secondary outcomes will include measures of acute care utilization and health related quality of life after conversion.

Primary Endpoint: This will be a descriptive study assessing the safety and benefit of converting subjects from full agonist opioids to buprenorphine. Data will be collected on need for hospitalization within 72 hours of conversion due to withdrawal induced VOC, as well as average COWS scores.

Secondary Endpoint: Measurement of quality of life, decrease in pain measured by the BPI and Promis pain tools decrease acute care utilization. In addition we will collect data from the 15-20 patients that have

already been converted to buprenorphine as part of routine care to formally examine utilization pre and post conversion.

3. Background

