- g. Definition of treatment failure or participant removal criteria. NA
- h. Description of what happens to participants receiving therapy when study ends or if a participant's participation in the study ends prematurely.
NA this is an observational trial.

5. Inclusion/Exclusion Criteria

a. Inclusion Criteria:

1. Has SCD, any genotype
2. Is being converted from full agonist opioid therapy to buprenorphine.
3. Able to provide consent
4. Is between the ages 18 and 100.

b. Exclusion Criteria:

1. Unwilling to sign consent.
2. Medical disorder, condition, or history that in the investigator's judgement would impair the patient's ability to participate or complete this study or render the patient to be inappropriate for enrollment.

6. Drugs/ Substances/ Devices

- a. The rationale for choosing the drug and dose or for choosing the device to be used.
NA
- b. Justification and safety information if FDA approved drugs will be administered for non-FDA approved indications or if doses or routes of administration or participant populations are changed. NA
- c. Justification and safety information if non-FDA approved drugs without an IND will be administered. NA

7. Study Statistics

- a. Primary outcome variable.
Primary Endpoint: This will be a descriptive study assessing the safety and benefit of converting subjects from full agonist opioids to buprenorphine. Data will be collected on need for hospitalization within 72 hours of conversion due to withdrawal induced VOC, as well as average COWS scores.
- b. Secondary outcome variables.
Secondary Endpoint: Measurement of quality of life and decreased pain measured by the BPI, ASCQ-Me, PROMIS Pain Interference, PROMIS Physical Function and decreased acute care utilization.
- c. Statistical plan including sample size justification and interim data analysis.
Descriptive study: Paired t-test will be used to compare patient's results on surveys and acute care utilization pre- and post- conversion.
- d. Early stopping rules.
NA

8. Risks

- a. Medical risks, listing all procedures, their major and minor risks and expected frequency.
- b. Participants may feel uncomfortable filling out surveys. Steps taken to minimize the risks.
Participants can stop filling out surveys at any time.
- c. Plan for reporting unanticipated problems or study deviations.
All study deviations and adverse events will be reported to the IRB.
- d. Legal risks such as the risks that would be associated with breach of confidentiality. NA

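### The retrospective cohort is selected on having been converted, so uncompleted attempts may go uncounted, and its surveys have no pre-conversion value

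*Combined protocol and SAP*

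**What the plan says.** The plan has two groups with different entry rules.

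- **Retrospective group.** Study design item 7 states: "We will also collect data on the 15-20 patients that we have now converted to buprenorphine". The secondary endpoint in section 2 describes them as patients who have "already been converted to buprenorphine as part of routine care to formally examine utilization pre and post conversion". The charts are to supply genotype, "acute care utilization (ED, sickle infusion clinic and hospitalizations"), and "COWS scores, sex, age and any complications that occurred with conversion". Item 7 then adds: "These subjects will be asked to complete ASCQ-Me and Promis tools".
- **Prospective group.** Inclusion criterion 2 in section 5 is "Is being converted from full agonist opioid therapy to buprenorphine". These participants complete the surveys within 90 days before day 0 and again on day 0: "Subject will complete ASCQ-Me, PROMIS Pain Interference, PROMIS Physical Function, and BPI with 7 day anchor (R").

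Section 7c names one analysis, a paired t-test of survey results and acute care utilization before and after conversion. It makes no separate provision for the retrospective group. The study procedures item on treatment failure and participant removal is marked NA.

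**The concern.** A prospective participant enters while the conversion is under way. A retrospective patient enters because the conversion has already taken place. If the team applies the word *converted* to completed conversions, a patient who took a first dose and did not get through the switch is in neither the numerator nor the denominator.

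That matters because this group is meant to inform on safety (COWS scores and complications of conversion) as well as on utilization. The study's primary safety outcome is hospitalization within 72 hours for withdrawal-induced VOC. An event of that kind could itself end an attempt, so the patients at risk of being left out are those most informative about safety. With 15 to 20 patients, one or two missing charts can change the message.

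The surveys raise a second, smaller matter. Their main use in the plan is a before-and-after comparison, and for this group there is no before.

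**Working it through.** The documents state no event rate, effect size or sample-size calculation for this cohort, so there is no figure of the plan to reproduce. The check has three steps.

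**1. Who is counted**

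| | Retrospective (section 2; study design item 7) | Prospective (section 5) |
|---|---|---|
| Entry | conversion has happened | conversion is happening |
| Date window | none stated | enrolment period of the study |
| Consecutive cases required | not stated | not at issue |
| Rule for uncompleted attempts | none stated | entry does not depend on completion |

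No other text fills the gap, since treatment failure is NA. A portion of text between the Background and the study procedures was not available for this check. If it says how the 15–20 were identified, that would settle the matter.

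**2. What an omission could do (illustration only)**

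Inputs: n = 15 or 20 converted patients, from item 7. Assumptions not in the documents: no events among the n, and k omitted attempts, each with an event. The rate moves from 0/n to k/(n + k). Limits are exact (Clopper-Pearson); for zero events the upper limit is 1 − 0.025^(1/n), which gives 16.8% for n = 20 and 21.8% for n = 15.

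| k (assumed) | n = 20 | n = 15 |
|---|---|---|
| 0 | 0/20 = 0% (0–16.8%) | 0/15 = 0% (0–21.8%) |
| 1 | 1/21 = 4.8% (0.1–23.8%) | 1/16 = 6.25% (0.2–30.2%) |
| 2 | 2/22 = 9.1% (1.1–29.2%) | 2/17 = 11.8% (1.5–36.4%) |
| 3 | 3/23 = 13.0% (2.8–33.6%) | 3/18 = 16.7% (3.6–41.4%) |
| 5 | 5/25 = 20.0% (6.8–40.7%) | 5/20 = 25.0% (8.7–49.1%) |

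For utilization, suppose the omitted patients had no change (also an assumption). The mean change over all starters is then n/(n + k) times the mean change among the converted. With k = 2 this is 20/22 = 0.91 or 15/17 = 0.88. Over k = 1 to 5 it runs from 0.95 to 0.80 for n = 20, and from 0.94 to 0.75 for n = 15.

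**3. What the surveys can support**

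A paired test needs a value before and a value after in the same person. Item 7 asks these patients to complete the ASCQ-Me and PROMIS tools once they have been converted, and its chart-review list contains no earlier survey. Usable survey pairs under the plan as written: 0 of 15–20. The utilization comparison is not affected in this way, because charts can supply pre-conversion values.

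**The case against.** The strongest reply is that *converted* reads more naturally as the induction event than as its success. The primary endpoint counts hospitalization within 72 hours of conversion, so a patient can be converted and then be admitted in withdrawal. Item 7 looks for complications in this same group, so it expects some bad courses among its members. This stands against a stronger reading that a reader might infer: that everyone who was admitted, went back to full agonists, died or left care is outside the cohort. Nothing requires a patient to be still on buprenorphine, alive or in care, and chart review can capture all of these. What stays open is the attempt that never became a conversion.

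A reader might also infer that the results are already biased. The documents do not show that any uncompleted attempt occurred, and the illustration is close to a worst case, with every omitted patient having the event and none of the others.

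On the surveys, a reader might infer that these patients are surveyed only once, or that their scores will be mixed with the prospective data so that different people are compared before and after. The text says neither, and a paired test would drop anyone without a pre-conversion value.

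Finally, the cohort sits under a secondary endpoint of a descriptive study, and the prospective cohort does not share the entry problem. That limits the consequence. It does not remove the need to say who is in the denominator.

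**Conclusion.** The point holds in a conditional form. The cohort is selected on having been converted, with no date window and no consecutive-case rule, so patients who started buprenorphine without completing conversion may be left out of its COWS, complication and utilization results. The bias arises only if such patients exist, are omitted, and had more complications or less improvement than the rest. Complication rates would then be too low and the utilization benefit too high. The size is unknown. Under the stated assumptions, two omitted cases would turn an observed 0% into about 9% to 12%. If the team already counts everyone who started, one sentence saying so would resolve this part.

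The survey part needs no assumption about failed attempts. As written, the cohort contributes no pairs to the section 7c test, and its scores can be reported only as post-conversion values.

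**What to change.** Reword item 7, and the matching sentence in section 2, as follows:

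- Define the retrospective cohort as all consecutive patients given a first buprenorphine dose for conversion at the clinic between two fixed dates, whatever happened next.
- Use that number as the denominator for complications and utilization.
- State how many did not complete conversion and how many were not surveyed.
- Report this cohort separately from the prospective one.
- In section 7c, leave its surveys out of the paired t-test and show them as cross-sectional post-conversion scores with time since conversion.

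The cost is a search of clinic records for first doses and a few more charts to abstract. It adds no study visits and changes no treatment. The downside is that the safety and benefit figures may look less favourable.

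### The stated primary safety summary leaves out 72-hour acute care without admission and admissions attributed to other causes, and an average COWS can mask a few high scores

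*Combined protocol and SAP*

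**What the plan says.** Section 2 (Objectives) sets the aim: "The primary outcome will be to assess the safety of the protocol". The Primary Endpoint text there, repeated in Section 7a, gives that aim two components: "Data will be collected on need for hospitalization within 72 hours of conversion due to withdrawal induced VOC, as well as average COWS scores".

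The other places that bear on early safety are these:

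- Study design, item 3b, schedules the first COWS on day 0: "Prior to discharge from SCIC subject will have COWS assessment, pain rating collected". Item 4 schedules the second on day 1: "Subject will return to repeat COWS".
- Item 5 collects acute care utilization at follow-up from day 14 on. Item 6 adds: "Data will be extracted from EPIC and CRISP on health care utilization for the 6 months prior to enrollment and 3 years post conversion".
- Section 7b makes utilization a secondary outcome, and Section 7c compares it before and after conversion by paired t-test. Section 7c states no analysis for the 72-hour count or for COWS, and gives no sample size.
- Item 7, for the 15-20 patients already converted, spells out "acute care utilization (ED, sickle infusion clinic and hospitalizations" and also asks for complications of conversion. Neither is spelled out for the prospective cohort.
- Section 8c sends adverse events to the IRB and plans no tabulation.

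**The concern.** The hospitalization component is restricted by setting (hospitalization) and by cause (withdrawal-induced VOC, with no visible rule for attribution). The COWS component is restricted to an average, and the visible text does not say whether that is over patients, over each patient's readings, or both.

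Outpatient treatment of early trouble is foreseeable at this site. Patients leave SCIC (read here as the infusion clinic) on day 0, and the protocol itself counts ED and infusion-clinic care as acute care in the retrospective cohort. Some withdrawal is also expected by design, since the pre-enrollment discussion covers "the need to be in mild- moderate withdrawal prior to initiating buprenorphine". The useful safety questions are therefore how many patients needed unplanned care in the first 72 hours, of what kind, and how many had high withdrawal scores. Followed as written, the primary summary answers the first only for attributed hospitalizations, and does not answer the last. In a descriptive study the stated summary is the safety result, and a table chosen after the data are seen is weaker evidence.

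**Working it through.** The plan gives no figure to reproduce: no prospective sample size, event rate or COWS value. The text can be checked directly; the numbers below only illustrate. N = 15-20 is the size of the retrospective group, the only patient number given. Event counts, visit rates and scores are assumed.

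**1. Which early event enters which stated summary**

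| Event in the first 72 hours | Primary count | COWS average | Other planned summary |
|---|---|---|---|
| Admission attributed to withdrawal-induced VOC | Yes | If present at a reading | Pre/post utilization |
| Admission attributed to another cause | No | If withdrawal present at a reading | Pre/post utilization, no 72-hour cut |
| ED or infusion-clinic visit, no admission | No, unless the undefined term need for hospitalization is read more widely | If withdrawal present at a reading | Pre/post utilization, no 72-hour cut |
| Withdrawal symptoms at the day 0 or day 1 reading | No | Yes | None |

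That prospective utilization includes ED and infusion-clinic visits is an inference from item 7.

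**2. Can the utilization comparison stand in?** The share of a post-conversion window taken up by 72 hours is 3 / window length in days:

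- first follow-up, day 14: 3/14 = 21%
- 6 months: 3/182.5 = 1.6%
- 3 years: 3/1,095 = 0.27%

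The documents do not say which windows the t-test compares, so none of these is the plan's own share. Over a window of months, an early rise could be offset by a later fall. For example, 2 extra early visits in 20 patients add 2/20 = 0.10 visits per patient. Against an assumed 3-12 visits per patient in 6 months, that is 0.10/3 = 3.3% down to 0.10/12 = 0.8%.

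**3. What the narrow count could show.** Suppose 1 patient is admitted with attribution and 2 others are treated without admission (Clopper-Pearson 95% intervals):

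| N | Attributed hospitalization | All three patients |
|---|---|---|
| 15 | 1/15 = 6.7% (0.2-31.9%) | 3/15 = 20.0% (4.3-48.1%) |
| 20 | 1/20 = 5.0% (0.1-24.9%) | 3/20 = 15.0% (3.2-37.9%) |

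The right-hand column leaves out background visits. Their expected number in 72 hours is N × annual rate × 3/365. At an assumed 6-24 visits per patient-year:

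- N = 20: 0.99 to 3.95 visits
- N = 15: 0.74 to 2.96 visits

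Under a Poisson assumption the share of patients with at least one background visit is 1 − exp(−rate × 3/365), or 4.8% to 17.9%. An all-cause excess of two patients is about the size of this background, so all-cause figures cannot be read alone.

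The chance that the narrow count reads zero is (1 − p·s)^N, where p is the share of patients with early harm and s the share of those admitted and attributed. At N = 20, p = 20% and s = 50%, 4 patients with harm and 2 counted are expected, and the chance of a zero count is 0.90^20 = 0.12. Over p = 10-30% and s = 25-75% it runs from 0.60 to 0.006.

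**4. What an average COWS can mask**

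- Across patients: (18 × 5 + 2 × 25)/20 = 7.0, the same as 20 patients at 7.
- Within a patient: (25 + 5)/2 = 15, the same as 15 on both days.
- One patient 20 points above the rest moves the mean over patients by 20/20 = 1.0 (N = 20) or 20/15 = 1.33 (N = 15).

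**The case against.** The strongest reply is that Section 7a uses collection language in a short IRB form for a descriptive, observational study. It does not say that nothing else will be reported, and giving a range or maximum beside a mean is ordinary practice. The utilization and COWS data are already collected, so a table can be added at analysis. This stands in part: the gap is in what is specified in advance, not in data capture.

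A reader might infer that all early harm managed without admission is missing from the primary result. The documents do not support that: both COWS readings fall within 72 hours and do not depend on admission, so withdrawal present then does enter the average. What is missing is acute-care visits without admission, admissions attributed elsewhere, and withdrawal arising outside the two readings.

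A reader might also take 1.6% or 0.27% as the dilution in the planned t-test, or a rate three times as high (15% against 5%) as the size of the understatement. Neither follows. The comparison windows are not stated, and the event counts are assumed and leave out background visits.

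Finally, part of the protocol was not available for review. The COWS reference is listed but cited nowhere in the visible text, so the scale was probably introduced there. The statistics section is visible and contains no COWS summary beyond the average, but this lowers confidence in any statement about what is absent.

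**Conclusion.** The point holds as a statement about the specified summary. Acute-care visits without admission and admissions attributed to other causes enter no visible 72-hour safety summary, and an average COWS alone can mask a few high scores. The pre/post utilization comparison, IRB reporting of adverse events and the retrospective complications item do not fill the gap.

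The actual size of the omission cannot be computed from the documents; the illustrations show only that it could matter with 15-20 patients. The conclusion assumes that need for hospitalization means roughly admission, that prospective utilization covers ED and infusion-clinic visits, and that the unavailable text adds no further summary. It is a worthwhile low-cost improvement, not evidence that safety data go uncollected.

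**What to change.** Keep the attributed hospitalization count and the 72-hour window. In Section 7, add:

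- A table of all-cause hospitalizations, ED visits and unplanned infusion-clinic visits in the same window, by type, excluding the planned day 0 and day 1 visits. Give the number of patients with at least one event, with exact 95% intervals, and the number of visits.
- For context only, the cohort's own background: visits in the 6 months before enrollment × 3/182.5.
- For COWS, a statement of what is averaged, the distribution at day 0 and at day 1, and each patient's highest recorded score, in addition to the average.

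The cost is one extra table and a few lines of text, from EPIC, CRISP and COWS data already collected. Separating planned from unplanned infusion-clinic visits takes some work, since the documents do not say that the distinction is recorded. The all-cause figures will include background visits, so they should stand beside the attributed count and not replace it.
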